***Important notes for the accurate assessment of temperature:***

Participants are to measure body temperature once per day, preferably always at the same time, and using the same standard unit of the considered country (Celsius or Fahrenheit) consistently. The optimal time for measurement is the evening, when body temperature is the highest. Temperature is also to be measured at the time of any apparent fever. The observed daily temperature and the route of measurement are to be recorded in the eDiary, and the highest temperature will be recorded by the site in the CRF. The preferred route for this study is oral.

**10.3.5.1.2 Serious and Non-serious Unsolicited AE Intensity Grading Scale**

For measurable unsolicited AEs that are part of the list of solicited reactions, the corresponding scale for solicited reactions will be used (see [Section 10.3.5.1.1](#)).

All other unsolicited AEs, including SAEs, will be classified according to the following intensity scale:

- Grade 1
  - CRF: A type of adverse event that is usually transient and may require only minimal treatment or therapeutic intervention. The event does not generally interfere with usual activities of daily living.
  - eDiary: No interference with activity.
- Grade 2
  - CRF: A type of adverse event that is usually alleviated with additional therapeutic intervention. The event interferes with usual activities of daily living, causing discomfort but poses no significant or permanent risk of harm to the research participant.
  - eDiary: Some interference with activity.
- Grade 3
  - CRF: A type of adverse event that interrupts usual activities of daily living, or significantly affects clinical status, or may require intensive therapeutic intervention.
  - eDiary: Significant; prevents daily activity.

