### ***Injection Site Reactions***

For each dose, the number and percentage of participants experiencing any injection site reaction after injection will be calculated.

The description of injection site reactions will be presented according to:

- **Solicited injection site reactions**

All solicited injection site reactions that occur each day within 7 days after injection will be summarized and presented.

- **Unsolicited injection site reactions**

All unsolicited injection site reactions after vaccination, reported within 21 days after each vaccination will be described according to the type of events.

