#### 4.2.2.2 Unsolicited AEs

##### 4.2.2.2.1 Presence

An observation will be considered an event if it has at least a verbatim term and is not a Grade 0 intensity event.

Grade 0 events are not included in safety analysis but are included in separate listings.

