##### 4.2.2.2.2 Intensity

Intensity will be derived according to the following classification: None, Grade 1, Grade 2, Grade 3, or missing.

If the unsolicited AE is measurable and its preferred term is part of the list of solicited reactions, then the measurement is derived based upon and following the same rule of the intensity scales defined in the protocol for that measurable injection site or systemic reaction. Note the intensity could be considered as "None" (not a reaction) in the analysis despite being considered a reaction by the investigator (e.g., swelling measurement  $> 0$  mm but  $< 25$  mm).

Intensity for the other unsolicited AEs will correspond to the value reported in the eCRF.

The maximum intensity corresponds to the highest intensity for a unique term.

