#### 4.2.3.6 Adverse Events Leading to Study Discontinuation

This information will be summarized as collected. A flag is available in the clinical database for all AEs to identify AEs leading to discontinuation before the end of active/intervention phase. In general, the items that are counted are:

- Disposition table: A participant who, on the “Completion at End of Active/intervention Phase” form question “What was the participant's status?” has “Adverse Event” checked.
- Safety overview table: A participant who has either on the “Completion at End of Active/intervention Phase” form, question “What was the participant's status?” has “Adverse Event” checked or lists a solicited AE that has “Caused Study Termination” checked that is at least Grade 1 or an unsolicited AE that has “Caused Study Discontinuation” checked that is at least Grade 1 or missing and is within the time-period indicated.
- System Organ Class (SOC)/Preferred Term (PT) table: A solicited AE that has “Caused Study Termination” checked that is at least Grade 1 or an unsolicited AE that has “Caused Study Discontinuation” checked that is at least Grade 1 or missing and is within the time-period indicated.

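### Measurable unsolicited AEs below the solicited Grade 1 cut-off go to a listing instead of the safety tables, and no exemption is written for records flagged serious, medically attended or causing discontinuation

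*Protocol*

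**What the plan says.** **Grading.** Protocol 10.3.5.1.2 applies to serious and non-serious unsolicited AEs alike. It says: "For measurable unsolicited AEs that are part of the list of solicited reactions, the corresponding scale for solicited reactions will be used". For the rest, "All other unsolicited AEs, including SAEs, will be classified according to the following intensity scale", and that scale is functional, runs from Grade 1 to Grade 3 and has no lower level. In protocol Tables 10.2 and 10.3, Grade 1 begins at 25 mm for erythema, swelling, induration and ecchymosis and at 38.0 °C (100.4 °F) for fever.

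**Derivation.** SAP 4.2.2.2.2 allows None, Grades 1 to 3, or missing. Its size and temperature rule is limited to AEs that can be measured and are coded to a solicited term. For these, "the measurement is derived based upon and following the same rule of the intensity scales defined in the protocol". The section gives a swelling of more than 0 but less than 25 mm as an example that may become None although the investigator regarded it as a reaction.

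**Inclusion.** SAP 4.2.2.2.1 counts an observation as an event only if it has a verbatim term and is not Grade 0. It adds: "Grade 0 events are not included in safety analysis but are included in separate listings". Under SAP 3.4.4.2.3 a missing unsolicited intensity stays missing, so that record is kept.

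**Flagged records.** SAP 4.2.2.2.6 identifies SAEs by the eCRF box, and SAP 4.2.3.3 reports seriousness as collected. Neither mentions the Grade 0 rule. SAP 4.2.3.6 counts discontinuations in the disposition and overview tables from the completion form. On the AE-record route, and in the SOC/PT table, it accepts an unsolicited AE only if it is one "that is at least Grade 1 or missing and is within the time-period indicated".

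**Protocol commitments.** Table 3.1 lists presence of unsolicited AEs, MAAEs and SAEs as endpoints with no grade threshold. Protocol 9.4.3 says: "All unsolicited injection site reactions after vaccination, reported within 21 days after each vaccination will be described according to the type of events". It also requires MAAE summaries by period. The SAP does not mention MAAEs.

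**The concern.** Seriousness, medical attendance and discontinuation are attributes of an event that its diameter or a thermometer reading does not measure. Under these rules the measurement decides whether the event is counted at all. An investigator could report a late-onset 20 mm induration, mark it as the reason for stopping or as serious, and the event would still not appear in the corresponding event table.

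Two features add weight. Protocol 10.3.1 treats every unsolicited injection-site event as related by default, so each injection-site record set aside also lowers the related count. The same section excludes solicited reactions from the MAAE definition, so an injection-site lesion that starts after the solicited window and prompts a doctor visit is exactly the kind of local event that can be an MAAE. If MAAE rules are added to the SAP without comment, they will take over the general unsolicited-AE definition.

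The tables affected feed the secondary safety objective and the choice of formulation after the main analysis.

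**Working it through.** The plan states no figure on this point, so there is none to reproduce. The check runs the rules on cases and then shows what one lost event does to an interval.

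**1. Reach.** There are nine solicited terms: five at the injection site and four systemic. Five are measurable: erythema, swelling, induration and ecchymosis (size) and fever (temperature). The other four (pain, headache, malaise, myalgia) have no level below Grade 1 on the protocol scale.

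**2. Grading and inclusion**, taking None as Grade 0:

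| Recorded value | Derived grade | Where it appears |
|---|---|---|
| 10 mm or 24 mm | None | listing only |
| 25 mm | Grade 1 | safety tables |
| 37.9 °C | None | listing only |
| 38.0 °C | Grade 1 | safety tables |
| missing | missing | safety tables |

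The link between None and Grade 0 is an inference. SAP 4.2.2.2.2 has no Grade 0, and SAP 4.2.2.2.1 does not mention None. If the two were different, the Grade 0 rule would refer to no level that the SAP defines. SAP 4.2.3.6 does not depend on the link, because it asks directly for Grade 1 or higher, or missing.

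**3. Discontinuation (SAP 4.2.3.6)** for an unsolicited AE with derived grade None:

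| Completion form shows AE | AE record flagged | Disposition | Overview | SOC/PT |
|---|---|---|---|---|
| yes | yes | counted | counted | not counted |
| no | yes | not counted | not counted | not counted |

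In the first row the tables do not reconcile: a participant stopped for an AE, but no term appears. In the second row the discontinuation is in none of the three tables.

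**4. Against the protocol.** Table 3.1 asks for presence of SAEs and MAAEs, and 9.4.3 asks for all unsolicited injection-site reactions within 21 days. Neither sets a grade floor. The SAP rule sets one for the five terms above.

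**5. Effect of one lost event (illustration only).** The method is the plan's own Clopper-Pearson interval: lower limit = 0.025 quantile of Beta(x, n − x + 1), or 0 if x = 0; upper limit = 0.975 quantile of Beta(x + 1, n − x). For x = 0 the upper limit reduces to 1 − 0.025^(1/n). The n are planned sizes: 50 (Group 3, one age stratum), 150 (Group 1 or 2, one stratum) and 150 + 150 = 300 (Group 1 or 2, both strata).

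| n | One event counted | Event in listing only |
|---|---|---|
| 50 | 2.0% (0.05 to 10.65) | 0% (0 to 7.11) |
| 150 | 0.67% (0.02 to 3.66) | 0% (0 to 2.43) |
| 300 | 0.33% (0.01 to 1.84) | 0% (0 to 1.22) |

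This shows what a single removal would do in a rare category. It does not estimate how often that happens.

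**The case against.** The strongest defence is consistency. SAP 4.2.2.1.1 treats a solicited swelling under 25 mm as None, and the unsolicited rule carries the same threshold past the solicited window. If every sub-threshold unsolicited event were tabulated, a 20 mm swelling starting on day 3 would not be a reaction, while one starting on day 9 would be a related AE. That argument stands for ordinary small late reactions, whose handling is a choice. It does not carry over to flagged records, because the flag expresses something that the size does not.

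A second defence is that a serious local event will rarely meet the conditions. Protocol 10.3.3 prefers a diagnosis to individual signs, and an event recorded as, say, an abscess falls on the functional scale, which has no level below Grade 1. This stands as to frequency, but it is not an exemption.

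Several stronger readings are tempting, and the documents do not support them:

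- **That the events are deleted.** They are moved to separate listings and remain reviewable.
- **That a participant who stops for such an event vanishes from every table.** The completion form still puts that participant in the disposition and overview tables, whatever the grade.
- **That AESIs are lost.** None of the conditions in protocol 8.3.6 is a measurable solicited term.
- **That every event set aside is related.** This is true by convention at the injection site. Unsolicited fever is systemic, and the investigator assesses its relationship.
- **That keeping a missing measurement while dropping a 20 mm one is itself an error.** Retaining unknowns is conservative and matches the SAP's treatment of missing relationship and missing onset.
- **That the SAP expressly drops MAAEs.** It has no MAAE rule at all. The effect follows only by default.

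**Conclusion.** The point holds in a limited form. Read together, protocol 10.3.5.1.2 and SAP 4.2.2.2.1 and 4.2.2.2.2 take an unsolicited erythema, swelling, induration or ecchymosis under 25 mm, or a fever term under 38.0 °C, out of the safety tables and leave it in a listing. No text exempts a serious record, and MAAE summaries would inherit the rule. This conflicts with the SAE and MAAE endpoints in protocol Table 3.1 and, for injection-site events, with protocol 9.4.3. For discontinuations the loss is partial: always from the SOC/PT table, and from all three tables only when the AE record alone carries the flag.

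The conclusion on the general tables assumes that None means Grade 0. The conclusion on discontinuations does not. The documents give no rate for these events, so the number affected cannot be estimated, and serious ones are probably rare. The case for a change is that a stated rule can remove protocol-endpoint events from the tables and is simple to correct, not that a large count is at stake.

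**What to change.** 1. In SAP 4.2.2.2.1 and 4.2.2.2.2, state how None relates to Grade 0.
2. In the same sections, state that any unsolicited AE flagged serious, medically attended or causing discontinuation is counted in the safety tables whatever its derived size or temperature grade. Carry this into the MAAE rules when the SAP adds the summaries that protocol 9.4.3 requires.
3. In SAP 4.2.3.6, remove the Grade 1 condition for unsolicited AEs flagged as causing discontinuation, so that the disposition, overview and SOC/PT tables reconcile.
4. For the remaining sub-threshold injection-site events, reconcile the SAP with protocol 9.4.3, for example with a separate row for events below Grade 1, or change the protocol wording to say that they are listed only.

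The cost is a few SAP sentences and at most one extra row in the table shells, with no new data. The downsides are slightly higher AE counts and, for flagged events, a small departure from the threshold used for solicited reactions, which a footnote can explain.

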## 10.4 Appendix: Contraceptive and Barrier Guidance

### 10.4.1 Definitions

#### ***Woman of Childbearing Potential (WOCBP)***

A woman is considered fertile following menarche and until becoming postmenopausal unless permanently sterile (see below).

If fertility is unclear (eg, amenorrhea in adolescents or athletes) and a menstrual cycle cannot be confirmed before first dose of study intervention, additional evaluation should be considered.

#### ***Women in the following categories are not considered WOCBP***

- 1) Premenarchal
- 2) Premenopausal female with 1 of the following:
  - Documented hysterectomy
  - Documented bilateral salpingectomy
  - Documented bilateral oophorectomy

For individuals with permanent infertility due to an alternate medical cause other than the above, (eg, mullerian agenesis, androgen insensitivity), investigator discretion should be applied to determining study entry.

Note: Documentation can come from the site personnel's: review of the participant's medical records, medical examination, or medical history interview.

- 3) Postmenopausal female
  - A postmenopausal state is defined as no menses for 12 months without an alternative medical cause.
    - A high follicle stimulating hormone (FSH) level in the postmenopausal range may be used to confirm a postmenopausal state in women not using hormonal contraception or hormonal replacement therapy (HRT). However, in the absence of 12 months of amenorrhea, confirmation with more than one FSH measurement is required.
    - Females on HRT and whose menopausal status is in doubt will be required to use one of the non-estrogen hormonal highly effective contraception methods if they wish to continue their HRT during the study. Otherwise, they must discontinue HRT to allow confirmation of postmenopausal status before study enrollment.

#### 10.4.2 Contraception Guidance

• CONTRACEPTIVESa ALLOWED DURING THE STUDY INCLUDE:

• Highly Effective Methodsb That Have Low User Dependency Failure rate of <1% per year when used consistently and correctly.

• Implantable progestogen-only hormone contraception associated with inhibition of ovulation

• Intrauterine device (IUD)

• Intrauterine hormone-releasing system (IUS)

• Bilateral tubal occlusion/ligation

• Azoospermic partner (vasectomized or due to a medical cause)

Azoospermia is a highly effective contraceptive method provided that the partner is the sole sexual partner of the woman of childbearing potential and the absence of sperm has been confirmed. If not, an additional highly effective method of contraception should be used.

Note: documentation of azoospermia for a male participant can come from the site personnel's review of the participant's medical records, medical examination, or medical history interview.

• Highly Effective Methodsb That Are User Dependent Failure rate of <1% per year when used consistently and correctly.

• Combined (estrogen- and progestogen-containing) hormonal contraception associated with inhibition of ovulation

– oral

– intravaginal

– transdermal

– injectable

• Progestogen-only hormone contraception associated with inhibition of ovulation

– oral

– injectable

• Sexual abstinence

Sexual abstinence is considered a highly effective method only if defined as refraining from heterosexual intercourse during the entire period of risk associated with the study intervention. The reliability of sexual abstinence needs to be evaluated in relation to the duration of the study and the preferred and usual lifestyle of the participant.



• Effective Methodsc That Are Not Considered Highly Effective Failure rate of ≥ 1% per year when used consistently and correctly.

• Progestogen-only oral hormonal contraception where inhibition of ovulation is not the primary mode of action

• Male or female condom with or without spermicide

• Cervical cap, diaphragm, or sponge with spermicide

• A combination of male condom with either cervical cap, diaphragm, or sponge with spermicide (double-barrier methods)

a) Contraceptive use by men or women should be consistent with local regulations regarding the use of contraceptive methods for those participating in clinical studies.

b) Failure rate of <1% per year when used consistently and correctly. Typical use failure rates differ from those when used consistently and correctly.

c) Considered effective, but not highly effective - failure rate of ≥ 1% per year.

Note: Periodic abstinence (calendar, symptothermal, post-ovulation methods), withdrawal (coitus interruptus), spermicides only, and lactational amenorrhea method (LAM) are not acceptable methods of contraception.

Male condom and female condom should not be used together (due to risk of failure from friction).

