#### Sex, contraceptive/barrier method and pregnancy testing requirements

**I03:** A female participant is eligible to participate if she is not pregnant or breastfeeding and one of the following conditions applies:

- Is of non-childbearing potential. To be considered of non-childbearing potential, a female must be post-menopausal for at least 1 year, or surgically sterile.

OR

- Is of childbearing potential and agrees to use a highly effective contraceptive method or abstinence from at least 4 weeks prior to each study intervention administration until at least 12 weeks after the last study intervention administration.

A female participant of childbearing potential must have a negative highly sensitive pregnancy test (urine or serum as required by local regulation) within 24 hours before the first dose of study intervention

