#### **8.3.5 Pregnancy**

Pregnant women are not eligible to participate in the study and women of childbearing potential agree to use an effective contraceptive method, as defined in the inclusion criteria. However, a participant could potentially become pregnant during her participation.

- Details of all pregnancies in female participants will be collected in the GPV database after the start of study intervention and until delivery in the GPV database.
- If a pregnancy is reported, the investigator should promptly inform the Sponsor and will record pregnancy information together with the contraceptive method on the appropriate form and submit it to the Sponsor within 1 month of learning of the pregnancy.
- While pregnancy itself is not considered to be an AE or SAE, any pregnancy complication or elective termination of a pregnancy for medical reasons will be reported as an AE or SAE.
- Abnormal pregnancy outcomes (eg, spontaneous abortion, fetal death, stillbirth, congenital anomalies, ectopic pregnancy) are considered SAEs and will be reported as such.
- The participant will be followed to determine the outcome of the pregnancy. The investigator will collect follow-up information on the participant and the neonate and the information will be forwarded to the Sponsor. Generally, follow-up will be required for at least 6 months to 1 year beyond the estimated delivery date, but will be in accordance with local regulations.

Any termination of pregnancy will be reported, regardless of fetal status (presence or absence of anomalies) or indication for the procedure.

- Any post-study pregnancy-related SAE considered reasonably related to the study intervention by the investigator will be reported to the Sponsor as described in [Section 8.3.4](#). While the investigator is not obligated to actively seek this information in former study participants, he or she may learn of an SAE through spontaneous reporting.
- Any female participant who becomes pregnant while participating in the study will discontinue study intervention until delivery or until delivery and end of lactation. However, the participant will be followed for safety assessment (and may be followed for immunogenicity assessment, if applicable).

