Per-protocol analysis set (PPAS)	
To be able to compare and present the results of immunogenicity in the same table, only one PPAS will be derived in this study.
 
Subset of the FAS participants who have provided D22 and D43 blood samples. Participants presenting with at least one of the following relevant protocol conditions will be excluded from the PPAS:
 

• Participant did not meet all protocol-specified inclusion criteria or met at least one of the protocol-specified exclusion criteria

• Participant did not complete the vaccination schedule

• Participant received a vaccine other than the one that he / she was randomized to receive

• Preparation and / or administration of vaccine was not done as per-protocol

• Participant did not receive vaccine in the proper time window

• Participant did not provide a post-dose serology sample at D22 (+7 days) and D43 (+7 days) in the proper time window or a post-dose serology sample was not drawn

• Participant received a medication impacting or that may have an impact on the immune response as described in Section 6.8

• Re-randomized participants

 
Any other deviation identified during the study conduct and judged by the clinical team during data review as having a potential impact on the assessment of immunogenicity will be used to exclude a participant from the PPAS.
 
Participants with missing SN data or participants with no valid test results of SN will be included in PPAS if they meet all the other requirements to be included in PPAS for HIH.
 
In the event of a local or national immunization program with a SARS-CoV-2 or other vaccine, participants who receive 1 or more doses of the vaccine listed above at any time during the study will not be withdrawn from the study.

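### Inclusion criterion I03 requires highly effective contraception, but Appendix 10.4.2 lists methods it labels not highly effective as allowed during the study, with no limit on when they may be used

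*Protocol*

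**What the plan says.** Protocol 5.1, criterion I03, admits a woman of childbearing potential who "agrees to use a highly effective contraceptive method or abstinence from at least 4 weeks prior to each study intervention administration" and continues "until at least 12 weeks after the last study intervention administration". It names no methods and does not refer to the contraception appendix.

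Protocol 10.4.2 names the methods. One heading, contraceptives "ALLOWED DURING THE STUDY INCLUDE", governs three groups: highly effective with low user dependency, highly effective but user dependent, and a third group of effective methods "That Are Not Considered Highly Effective". The third group contains condoms, barrier devices with spermicide, and progestogen-only pills that do not work mainly by inhibiting ovulation. Footnote c repeats its status: "Considered effective, but not highly effective". The closing note rules out some other methods, and none of the third group is among them.

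Protocol 8.3.5 states that "women of childbearing potential agree to use an effective contraceptive method, as defined in the inclusion criteria".

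Protocol 9.3 excludes a participant from the PPAS if "Participant did not meet all protocol-specified inclusion criteria or met at least one of the protocol-specified exclusion criteria"; SAP 3.3 has the same condition. Protocol section 5 permits no eligibility waivers.

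**The concern.** The appendix is the only place where a site can look up which methods count, so in practice it is the tool for applying I03. It places a group below the I03 standard under the same allowed heading as the groups that meet it, and gives no rule for when the third group is acceptable.

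Two things are at stake. The first is a participant-safety rule for an investigational vaccine, applied by site staff at enrolment. The second is classification in the analysis: a woman enrolled in line with the appendix may later be found not to meet I03, and that finding removes her from the PPAS. Two people reviewing the same record could reach different answers.

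**Working it through.** No formula applies to the contradiction itself, and the plan gives no figure to reproduce. The check is a comparison of the texts.

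**Standard required**
- I03: highly effective method or abstinence.
- 10.4.2, groups 1 and 2: failure rate below 1% per year with consistent and correct use. These are labelled highly effective.
- 10.4.2, group 3: failure rate of 1% or more per year. This group is labelled not highly effective, yet sits under the allowed heading.
- 8.3.5: effective, with a pointer to the inclusion criteria.

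On the appendix's own threshold, a woman whose only method is in group 3 does not meet I03 but is using a method that the appendix allows.

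**Period covered**
- I03: at least 4 weeks before each dose to at least 12 weeks after the last. With dose 2 on D22, the minimum end is 22 + (12 × 7) = D106. With dose 2 at the end of its +7-day window (D29), it is 29 + 84 = D113.
- 10.4.2: the study, with no start or end stated. The last visit is D387, with a window of +14 days.

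The appendix period therefore includes the whole dosing phase and the 12 weeks after it, where I03 asks for more. The two periods separate only after about D106 to D113, and the text does not confine group 3 to that later part.

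**Cross-references**
- I03 does not cite 10.4.2, and 10.4.2 does not cite I03.
- Footnote a of 10.4.2 defers to local regulations and does not say which groups satisfy I03.
- 8.3.5 cites the inclusion criteria but leaves out the word highly. In 10.4.2, effective without highly is the label of group 3.

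**Consequence in the analysis**
- A woman enrolled on a group 3 method alone does not meet I03. No waiver is possible, so she is an eligibility deviation and, under Protocol 9.3 and SAP 3.3, a PPAS exclusion.
- The FAS requires randomization, at least one dose and a D22 or D43 blood sample. It has no eligibility condition, so she stays in it.
- The sample size and the Table 9.2 probabilities do not depend on the contraception rule.

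**Number affected**
- This is not in the documents. The 18-64 stratum is planned at 150 + 150 + 50 = 350, but that count includes men, postmenopausal women and surgically sterile women. It is a loose ceiling, not an estimate.

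**The case against.** The strongest reply is that I03 settles the matter. Section 5.1 makes eligibility conditional on every inclusion criterion, waivers are barred, and section 8 requires sites to confirm all eligibility criteria. The appendix is headed as guidance, states no enrolment rule, and labels group 3 plainly as below the standard that I03 names. A careful site reading both would see that a condom alone does not satisfy I03. This stands in part. A reader might infer that eligibility is defined in two ways, or that sites would enrol women whom I03 excludes. The documents do not support either: I03 is the formal rule, and the appendix creates only the possibility of error. Nor does 8.3.5 set a further standard, since it points back to I03.

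A second reply is that group 3 is meant for the part of the study after the I03 window closes. That would remove the conflict, but the protocol does not say it, and the appendix heading has no time limit.

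A third reply is that little follows for the analysis. Agreement on contraception is given before randomization, so these exclusions should not depend on arm. Every immunogenicity variable is also analysed on the FAS, and no hypothesis is tested. This stands. A reader might infer biased dose comparisons or a material loss from the PPAS; nothing in the documents supports either.

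Finally, a reader might infer that protection against exposure in pregnancy rests on this rule alone. It does not. The protocol requires a pregnancy test before each vaccination, stops further vaccination after a positive test, and follows pregnancies to outcome. These safeguards do not replace contraception after the second dose, so the wording still matters.

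**Conclusion.** The inconsistency is real and lies in the protocol's wording. I03 and Appendix 10.4.2 set different levels over an overlapping period, and 8.3.5 uses the looser word while citing the stricter criterion. I03 formally governs, so the defect is that the only list of methods could lead a site to enrol a woman who does not meet it.

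The size cannot be stated. It is confined to women of childbearing potential whose only method is in the third group. For each such enrolment the consequence is one eligibility deviation and one PPAS exclusion; the FAS, sample size and Table 9.2 do not change. This rests on reading 10.4.2 as written, without an implied time limit, and on applying the PPAS eligibility condition literally. The point merits correction because it concerns a safety rule used at enrolment, not because it threatens the immunogenicity results.

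**What to change.** Reconcile Protocol 5.1 (I03), 8.3.5 and 10.4.2 so that one stated set of permitted methods, with its time window, applies both to eligibility and during the study. Have I03 and 8.3.5 cite that list directly. If different methods are meant to be acceptable at different times, state the times. Use the same set when judging I03 for the PPAS under Protocol 9.3 and SAP 3.3. Which set applies is for the sponsor and the ethics board to decide.

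The cost is wording in a protocol amendment and matching site guidance. No design, sample size or analysis method changes.
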